5.4.1.2. Epacadostat

Doses of epacadostat may need to be decreased because of toxicity, or interrupted and restarted with recovery of laboratory values or AEs. See also [Table 9](#).

5.4.1.3. Pembrolizumab

In Phase 1 and Phase 2 Part A, pembrolizumab may be interrupted, but no dose modifications are permitted. In all cases where pembrolizumab dosing is held, dosing for INCB001158 and epacadostat must also be held. However, if either or both of INCB001158 and epacadostat is/are discontinued due to drug-related AEs, subjects are allowed to continue to receive the other study treatments. See also [Table 9](#).

5.4.2. Dose-Limiting Toxicity and Determination of Maximum Tolerated Dose in Phase 1

Dose-limiting toxicity will be defined as the occurrence of any of the toxicities in [Table 8](#) occurring up to and including Day 42, except those with a clear alternative explanation (eg, disease progression) or transient (≤ 72 hours) abnormal laboratory values without associated clinically significant signs or symptoms based on investigator determination. All DLTs will be assessed by the investigator using CTCAE v4.03 criteria. Subjects who receive at least 63 of 84 doses ($\geq 75\%$) for each of INCB001158 and epacadostat at the level assigned plus at least 2 doses of pembrolizumab or who have a DLT, will be considered evaluable for determining tolerability of the dose. Subjects who do not meet these criteria may be replaced to obtain sufficient evaluable subjects to be able to assess that dose level using the BOIN design, as outlined in [Table 2](#).

Clear evidence of urea cycle inhibition (eg, an increase in fasting urinary orotic acid to $> 10 \times \text{ULN}$, any orotic acid value of $> 40 \times \text{ULN}$, or symptomatic hyperammonemia) would also be considered a dose-limiting event and will be treated the same as a DLT with regard to the dose escalation rules and definition of the MTD described in Section 4.1.1. Refer to the INCB001158 IB ([iIB](#)) for an explanation of these orotic acid thresholds.

Individual subject dose reductions for INCB001158 and epacadostat may be made based on events observed at any time during treatment; however, for the purposes of dose cohort escalation/de-escalation, expanding a dose cohort, and determining the MTD of INCB001158, decisions will be made based on events that are observed from the first day of study treatment administration through and including the final day of Cycle 2 (Day 42). A lower MTD may subsequently be determined based on relevant toxicities that become evident after Day 42.

If a subject experiences a DLT that is considered life-threatening, permanently discontinue all 3 study treatments. If a subject experiences a DLT that is not considered life-threatening, interrupt all 3 study treatments, and follow the management guidelines in [Table 9](#).

Table 8: Definition of Dose-Limiting Toxicity

Toxicity
Nonhematologic

 • Any \geq Grade 3 nonhematologic toxicity EXCEPT: 
 – Transient (\leq 72 hours) abnormal laboratory values without associated clinically significant signs or symptoms. – Nausea, vomiting, and diarrhea adequately controlled with medical therapy within 48 hours. – An event clearly associated with the underlying disease, disease progression, a concomitant medication, or comorbidity. – Asymptomatic changes in amylase, lipase, or lipid profiles. – Singular or nonfasting elevations in blood glucose (ie, blood glucose excursions will be considered toxicities if fasting blood glucose is elevated on 2 separate occasions).
Hematologic

 • Grade 3 thrombocytopenia with bleeding. • Grade 4 thrombocytopenia. • Febrile neutropenia (ANC $<$ $1.0 \times 10^9/L$ and fever $>$ $101^\circ F/38.5^\circ C$). • Grade 4 neutropenia that does not recover to \leq Grade 2 in \leq 7 days after interrupting study treatment. • Grade 4 anemia.
Immune-related toxicity

 • \geq Grade 2 ocular irAEs will be considered a DLT. • Grade 3 irAEs that do not improve to baseline or at least Grade 1 in $<$ 5 days with appropriate care or with corticosteroid therapy will be considered a DLT. Exception: Grade 3 rash in the absence of desquamation, no mucosal involvement, does not require systemic steroids, and resolves to Grade 1 by the next scheduled dose of pembrolizumab or 14 days, whichever is longer. • Grade 4 irAEs will be considered a DLT regardless of duration. • \geq Grade 2 pneumonitis.
General

 • The inability to receive \geq 75% of INCB001158 and/or epacadostat doses and/or 2 doses of pembrolizumab during the DLT-evaluation period (42 days) due to a drug-related AE will be considered a DLT. • Any other AE that is felt to be treatment-limiting in the medical opinions of the principal investigator and the medical monitor may be considered a DLT.

ANC = absolute neutrophil count.

Note: Transient (\leq 72 hours) abnormal laboratory values without associated clinically significant signs or symptoms based on investigator determination will not be considered a DLT.

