^a -1 dose level to be used if unacceptable toxicity is observed at Dose Level 1 and is deemed to be due to epacadostat
^b -1 dose level to be used if unacceptable toxicity is observed at Dose Level 1 and is deemed to be due to INCB001158.

A PAD will be defined as a dose at or below the monotherapy MTD at which at least half of the subjects (and at least 2 subjects in total) enrolled at a particular dose level achieve a trough (C_{min}) plasma concentration of INCB001158 at steady state of $\geq 1 \mu M$, which is equivalent to the IC_{90} for arginase 1. This definition may be modified based on emerging data from the INCB 01158-101 first-in-human study, upon agreement between the medical monitor and the study investigators. The MTD, if reached, is the maximum tested dose of INCB001158, such that no more than 33% of the subjects receiving the triplet combination experience a DLT during the first 6 weeks on study drug.

After completing the dose escalation per the BOIN rules, one of the INCB001158 dose levels that is pharmacologically active (ie, a PAD) and tolerable in combination with epacadostat 100 mg BID or lower and pembrolizumab 200 mg Q3W (ie, MTD or lower) will be selected, and that triplet combination will be the RP2D. The doublet RP2D would consist of the same doses of INCB001158 and epacadostat.

Note that if a dose level to be assigned as RP2D has fewer than 9 evaluable subjects in it, then the medical monitor and study investigators can consider adding subjects to a total of 9 before making the final RP2D decision.

At the discretion of the sponsor, up to a total of 6 additional "backfill" subjects may be enrolled at any tolerable dose level to further investigate safety

Phase 2 – Tumor Expansion: In the tumor expansion parts (A and B), each tumor cohort will be assessed for the safety and tolerability of the RP2D of the respective combinations, as well as ORR using a Simon 2-stage design, to determine if the combinations have sufficient antitumor activity to warrant further testing in subsequent clinical studies. See Study Design figure for details of Phase 2 cohorts.

Study Design

Phase 1: Dose Escalation

[figure not shown]
[figure not shown]
Phase 1: INCB001158 + Epacadostat + Pembrolizumab Dose Escalation

- Escalate INCB001158 with fixed epacadostat (100 mg BID) and pembrolizumab (200 mg Q3W) doses
- Subjects with advanced/metastatic solid tumors who have failed all standard therapies

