6.2. Treatment

The treatment period begins on the day the subject receives the first dose of study treatment (Cycle 1 Day 1), as assigned in the IRT system, through the point at which the investigator determines the subject will be permanently discontinued from study treatment. Cycle 1 Day 1 must be no more than 21 days after the subject has signed the ICF. Dates for subsequent study visits will be determined based on this day and should occur within 3 days (\pm) of the scheduled date unless delayed for safety reasons. At Cycle 1 Day 1, results from screening visit evaluations should be reviewed to determine whether the subject continues to meet the eligibility requirements, as specified in the Protocol.

Subjects will have regularly scheduled study visits as outlined in [Table 14](#) and [Table 15](#), and toxicities will be monitored continuously and will be graded using the NCI CTCAE v4.03 criteria.

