7.6.5. Laboratory Assessments

A certified laboratory local to the study site and subject will perform most of the clinical laboratory assessments for safety (ie, chemistries, hematology assessments, coagulation panel, thyroid panel, lipid panel, and urinalysis). The investigative site will enter the laboratory results and laboratory normal ranges into the eCRF. All local laboratory assessments should be performed using standard procedures on the days indicated in [Table 15](#). [Table 16](#) lists the specific laboratory analytes required for each test. Some additional tests (ie, [REDACTED], [REDACTED]), plus urinary orotic acid; see [Table 16](#)) will be conducted by one or more central laboratories, on the days indicated in [Table 15](#).

Additional testing may be required by the sponsor based on emerging safety data. Additional tests may also be performed if clinically indicated.

Laboratory samples collected on study Day 1 must be performed before study treatment administration. After Cycle 1, predose laboratory procedures can be conducted up to 72 hours before study treatment administration (within the 3-day study window), and results should be reviewed by the investigator or qualified designee and found to be acceptable before a new cycle of treatment is initiated.

[REDACTED]

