7.6.5.2. Urinalysis

In addition to the standard urinalysis outlined in Table 16, urinary orotic acid levels will be assessed (see Table 17), as a marker of urea cycle inhibition, a potential side effect of INCB001158 (see Section 1.3.1). Subjects must fast at least 8 hours before each clinic visit and void their bladder in the morning before providing the predose urine sample at the clinic, as outlined in Table 17.

[REDACTED]

Table 17: Sample Collection Times for Urine Assessments of Orotic Acid

Study Visit ^a	Time
C1D1	Predose and 6 h (\pm 1 h) postdose
C1D8 ^b	Predose
C1D15	Predose and 6 h (\pm 1 h) postdose
C2D1 and D1 of all subsequent cycles	Predose

^a Additional samples may be collected as clinically indicated.

^b The C1D8 sample will not be collected for subjects enrolled in Phase 2.

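### Do the two timings in Section 5.4.2 (toxicities occurring, events observed, by Day 42) leave a silent laboratory event found at C3D1 without a place in the DLT count?

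*Combined protocol and SAP*

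**What the plan says.** Section 5.4.2 states the window twice. The definition covers Table 8 toxicities "occurring up to and including Day 42". A later sentence, on moving between dose levels, expanding a cohort and setting the MTD, relies on "events that are observed from the first day of study treatment administration through and including the final day of Cycle 2 (Day 42"). That sentence begins by contrasting these decisions with individual dose reductions, which may respond to "events observed at any time during treatment". The sentence after it adds: "A lower MTD may subsequently be determined based on relevant toxicities that become evident after Day 42". Orotic acid events (fasting value above 10 × ULN, or any value above 40 × ULN) count like DLTs for escalation.

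The synopsis and Section 4.1.1 define the MTD by the share of subjects who "experience a DLT during the first 6 weeks on study drug".

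On the schedule, cycles last 21 days and, after Cycle 1, visits fall on Day 1 only. Section 6.2 says of visits after C1D1: "Dates for subsequent study visits will be determined based on this day and should occur within 3 days", in either direction. Table 17 takes predose orotic acid at "C2D1 and D1 of all subsequent cycles". Section 7.6.5 lets predose samples be drawn up to 72 hours early and wants results "found to be acceptable before a new cycle of treatment is initiated".

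Under Amendment 2, Section 4.3.1 allows up to 5 subjects in Phase 1, and Section 4.6.1 does not open Phase 2.

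**The concern.** One sentence appears to sort events by when they happen, the other by when they are seen. For a toxicity with symptoms the two dates nearly coincide. For a silent laboratory abnormality they can differ by as much as the interval between draws, and here that interval spans most of Cycle 2. A value that turned abnormal on, say, Day 35 and was first measured on Day 43 meets the definition sentence but, taken literally, not the decision sentence. The protocol gives no rule for dating such an event.

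This matters in principle because DLTs are part of the Phase 1 primary endpoint and are the only input to Table 2. Silent events are also plausible for this drug: Section 1.2.4 reports 2 asymptomatic orotic acid events among 3 subjects at 150 mg BID in the first-in-human study, though at a lower threshold (5 × ULN) than the one used here. An omitted event lowers the count and so favors escalation.

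**Working it through.** **1. Calendar** (21-day cycles; 3-day visit window from Section 6.2)

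- C2D1 = 1 + 21 = Day 22, allowed Days 19 to 25.
- C3D1 = 1 + 2 × 21 = Day 43, allowed Days 40 to 46. Of these 7 days, 3 (Days 40 to 42) lie inside the window and 4 outside.
- Days after C2D1 with no guaranteed draw: 42 − 22 = 20 (20/42 = 47.6%). With the visit window on C2D1, the range is 42 − 25 = 17 to 42 − 19 = 23.
- Orotic acid samples through C2D1 (Table 17): 2 at C1D1, 1 at C1D8, 2 at C1D15, 1 at C2D1, so 6 samples at 4 visits. Sampling is weighted to Cycle 1.

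**2. Table 2 reproduced** (Section 9.5.1: target 0.33, lower 0.6 × 0.33 = 0.198, upper 1.4 × 0.33 = 0.462)

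- Escalation limit: ln(0.802/0.67) / ln[(0.33 × 0.802)/(0.198 × 0.67)] = 0.2604.
- De-escalation limit: ln(0.67/0.538) / ln[(0.462 × 0.67)/(0.33 × 0.538)] = 0.3947.
- Rounding n × 0.2604 down and n × 0.3947 up gives the escalation row for n = 3 to 9 and the whole de-escalation row. The elimination row follows from a Beta posterior (uniform prior assumed) with the 0.95 cutoff.

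**3. Effect of one uncounted event**

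| Evaluable | Counted | Not counted |
|---|---|---|
| 3 | 1: neither escalate nor de-escalate | 0: escalate |
| 4 | 2: de-escalate | 1: escalate |
| 5 | 2 (40%): de-escalate | 1 (20%): escalate |

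These switches would follow from losing any one DLT for any reason. They do not show that the wording loses one.

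**4. The two readings**

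- *Event timing.* The decision sentence uses the same verb for dose reductions at any time on treatment, where it simply means events that happen. The MTD wording in the synopsis and Section 4.1.1 is also event-timed. On this reading there is one window, and a C3D1 finding is placed by its judged onset.
- *Detection.* Events seen by Day 42 feed Table 2. Those that become evident later fall under the next sentence of Section 5.4.2 and may lower the MTD.

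Each reading gives the event a destination. They differ only for an event with onset judged to fall by Day 42 and first detection after it. For orotic acid even that overlap is thin: the event is defined by a measured value, so if the value is the event, it happens on the sampling day and both readings agree.

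**5. How many silent events qualify.** Table 8 excludes transient laboratory values (72 hours or less) and asymptomatic amylase, lipase or lipid changes. Grade 3 thrombocytopenia needs bleeding, glucose needs two fasting elevations, and Grade 4 neutropenia must fail to recover within 7 days of interrupting treatment. A single C3D1 draw cannot by itself establish the glucose or neutropenia criteria, or show that a value lasted more than 72 hours.

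**6. Who decides.** Investigators assess DLTs, and Sections 4.1.1, 5.4.5 and 8.8 have sponsor and investigators review cohort data together, adjudicate high-grade events and agree on escalation. An orotic acid value at the dose-limiting threshold leads to a treatment change under Table 9, which makes it an adverse event under Section 8.1.1. Section 9.4.2.1 lists all adverse events, so the finding stays visible whichever way it is counted.

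**7. What is left to decide.** If 5 is the Phase 1 total and one level takes 3 evaluable subjects, 5 − 3 = 2 remain, below the minimum of 3 for a second level.

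**The case for a change.** The best argument for a change is that the ambiguity can be reached in practice and the existing safeguards do not remove it. The retest in Table 9 needs an earlier abnormal value. Sampling early, on Days 40 to 42, is optional. Adjudication under Section 5.4.5 comes without a timing rule. The MTD sentence is permissive and does not address the Table 2 count. The dating convention in Section 8.1.2 is written for changes in severity, not for silent onset. Orotic acid goes to a central laboratory, so even a Day 42 sample may be reported later. Since having a DLT also makes a subject evaluable, the attribution can alter the denominator. Against all this, the cost would be a sentence or two.

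Much of that stands as description: the verbs differ, and no explicit attribution rule exists. It does not show a wrong result. The onset of a silent abnormality between two draws is unknown under any wording, so a rule would replace case judgment with a convention. Counting every C3D1 finding, for example, could bring in events that began on Days 43 to 46. Which convention is preferable is debatable, and it belongs to the sponsor and investigators. With at most 5 subjects at 4 planned sites, the group that applies Table 2 can examine each case directly.

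**Conclusion.** The plan does not need changing. Section 5.4.2 contains a wording mismatch that the people applying it can resolve sensibly, because the passages admit a consistent reading and late findings are not ignored under the alternative one. The exposure is limited to a silent laboratory event that meets Table 8 or the orotic acid thresholds, is judged to have begun by Day 42, and is first found on Days 43 to 46. Its frequency cannot be estimated: the documents give neither the share of DLTs that are silent nor their onset times.

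If one such event arose and were left out, the reported rate in a 5-subject cohort would be 20% instead of 40%. That would be visible in the listings and open to discussion. The conclusion assumes that the joint review takes place as described and that the limit of 5 is the Phase 1 total. Were escalation to resume with larger cohorts, harmonizing the wording would be a reasonable editorial step, with the timing criterion left to the sponsor and investigators.

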Dose escalation will begin with starting doses of INCB001158 at least 2 dose levels below the maximum tolerated and tested dose from the INCB 01158-101 study (likely to be 50 mg BID or 75 mg BID – see [Table 3](#) and [Table 4](#), respectively). If the starting dose is not one of those 2 dose levels, then a revised dose escalation table will be provided to sites. However, the starting doses of epacadostat (100 mg PO BID continuous dose administration) and pembrolizumab (200 mg IV Q3W) will not be changed. Epacadostat 100 mg BID was selected as the starting dose because it has been shown to be active and tolerable in several epacadostat combination clinical studies, including with pembrolizumab ([eIB](#), [Gangadhar et al 2017](#), [Hamid et al 2017a](#), [Hamid et al 2017b](#), [Smith et al 2017](#)). The starting dose of pembrolizumab is the standard, approved dose and schedule ([Keytruda PI](#), [Keytruda SPC](#)) and also the dose used in combination with epacadostat in Phase 3.

If the starting doses of the triplet combination of INCB001158, epacadostat, and pembrolizumab are tolerable (eg, none of the first 3 evaluable subjects experiences a DLT; see [Section 5.4.2](#)),

then the INCB001158 dose will be escalated in subsequent cohorts, while keeping the epacadostat and pembrolizumab doses constant, until one of the stopping rules (described above and in [Table 2](#)) is met.

If the starting doses of INCB001158, epacadostat 100 mg BID, and pembrolizumab 200 mg Q3W are not tolerable, then an additional cohort will be enrolled at a reduced dose of either INCB001158 or epacadostat, depending on which one is deemed most likely to have caused the intolerability, upon agreement between the medical monitor and the study investigators (ie, Dose Level -1A or -1B; see [Table 3](#) and [Table 4](#)).

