4.3. Number of Subjects

4.3.1. Planned Number of Subjects

Under Protocol Amendment 2, up to 5 subjects will be enrolled in the dose-escalation (Phase 1) part. No subjects will be enrolled in Phase 2.

It is planned to have 4 sites during Phase 1.

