5.2.1.3. Storage

Blister cards of INCB001158 capsules should be stored at room temperature, 15°C to 30°C (59°F to 86°F).

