5.2.3.3. Storage

Vials of pembrolizumab must be stored under refrigeration at 2°C to 8°C (36°F to 46°F) in the original carton to protect them from light. Do not freeze. Do not shake.

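### Table 8's fever limit for the febrile-neutropenia DLT pairs 101 °F with 38.5 °C, which are not equal, and does not say which governs (very small practical impact)

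*Combined protocol and SAP*

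**What the plan says.** Table 8, in Section 5.4.2, lists febrile neutropenia among the hematologic DLTs. It requires ANC below 1.0 × 10⁹/L together with "fever $>$ $101^\circ F/38.5^\circ C". The two temperatures are joined by a slash. There is no indication that one is approximate, and no governing unit is named.

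Section 5.4.2 adds that "All DLTs will be assessed by the investigator using CTCAE v4.03 criteria". It quotes no CTCAE temperature and does not say that CTCAE overrides Table 8. Table 8 also has a discretionary route to DLT status: "Any other AE that is felt to be treatment-limiting in the medical opinions of the principal investigator and the medical monitor may be considered a" (the quoted sentence ends with the term DLT).

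The DLT count drives the dose rules in Section 4.1.1, where the example of a tolerable starting dose is that "none of the first 3 evaluable subjects experiences a DLT". Under Amendment 2, Section 4.3.1 states that "up to 5 subjects will be enrolled in the dose-escalation (Phase 1) part", and Section 4.6.1 closes enrollment except for subjects already in screening on 08 MAY 2018.

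**The concern.** A DLT criterion is a yes/no rule, and this one gives two different answers over a short range of temperatures. A site that works in Fahrenheit would reasonably apply 101 °F as printed; a site that works in Celsius would apply 38.5 °C. The same event could be a DLT at one site and not at the other.

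Three things follow from the label:

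- **DLT count.** DLTs are a component of the Phase 1 primary endpoint (Section 2, Table 1) and the input to Table 2.
- **Interruption.** Section 5.4.2 requires all three treatments to be interrupted for a DLT that is not life-threatening. Without the label, interruption is discretionary.
- **Growth factors.** Section 5.6.3 does not permit agents such as G-CSF and GM-CSF in the first cycle unless the subject has a hematologic DLT.

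**Working it through.** **Inputs.** Fever limit: 101 °F and 38.5 °C (Table 8). Other paired temperatures: 15–30 °C with 59–86 °F (Sections 5.2.1.3 and 5.2.2.3) and 2–8 °C with 36–46 °F (Section 5.2.3.3). Target DLT rate 0.33 with multipliers 0.6 and 1.4 (Section 9.5.1). Doublet safety data on 294 subjects (Section 1.3.4).

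**Step 1: convert the pair.** With C = (F − 32)/1.8 and F = 1.8 × C + 32:

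- (101 − 32)/1.8 = 38.33 °C
- 1.8 × 38.5 + 32 = 101.3 °F
- gap: 38.50 − 38.33 = 0.17 °C, or 0.3 °F

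The printed pair is not reproduced exactly. It is reproduced only if 101.3 °F is rounded to a whole degree.

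**Step 2: find the readings on which the two limits disagree.**

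| Reading | Equivalent | Above 101 °F | Above 38.5 °C |
|---|---|---|---|
| 38.3 °C | 100.94 °F | no | no |
| 38.4 °C | 101.12 °F | yes | no |
| 38.5 °C | 101.30 °F | yes | no |
| 38.6 °C | 101.48 °F | yes | yes |
| 101.0 °F | 38.33 °C | no | no |
| 101.1 °F | 38.39 °C | yes | no |
| 101.2 °F | 38.44 °C | yes | no |
| 101.3 °F | 38.50 °C | yes | no |
| 101.4 °F | 38.56 °C | yes | yes |

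Two readings on a 0.1 °C scale and three on a 0.1 °F scale fall in the disputed band.

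**Step 3: test the rounding explanation.** The refrigerated range is rounded: 2 °C = 35.6 °F, shown as 36, and 8 °C = 46.4 °F, shown as 46. The room-temperature range converts exactly (15 °C = 59 °F, 30 °C = 86 °F), so it does not discriminate. Rounding is consistent with 38.5 °C being the intended value but does not prove it: 38.3 °C = 100.94 °F also rounds to 101. The protocol's other body temperatures are in Celsius only (41 °C in Table 11; 38 °C and 35.5 °C in Table 23), which also points to 38.5 °C.

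**Step 4: what one DLT can change in the escalation rule.** With φ = 0.33, φ₁ = 0.6 × 0.33 = 0.198 and φ₂ = 1.4 × 0.33 = 0.462:

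- escalation cut-off = ln[(1 − φ₁)/(1 − φ)] / ln[φ(1 − φ₁)/(φ₁(1 − φ))] = 0.2604
- de-escalation cut-off = ln[(1 − φ)/(1 − φ₂)] / ln[φ₂(1 − φ)/(φ(1 − φ₂))] = 0.3947

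These reproduce the escalation and de-escalation counts in Table 2 for 3 to 9 subjects. With 3 subjects, 0.2604 × 3 = 0.78 and 0.3947 × 3 = 1.18, so 0 DLTs means escalate, 1 means stay and 2 means de-escalate. In principle one relabelled event moves a cohort by one category.

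**Step 5: how likely an in-band event is.** The documents give neither a febrile-neutropenia rate for the triplet nor a distribution of peak temperatures. Section 1.3.4 lists the treatment-related events of Grade 3 or higher seen in more than 3 of 294 doublet subjects, and febrile neutropenia is not among them. If it would have been graded 3 or higher, the observed count was at most 3, and 3/294 = 1.02%. Assume that the triplet rate is no higher. If every case peaked inside the band, the chance of at least one among 5 subjects would be 1 − (1 − 3/294)⁵ = 5.0%. If none did, it would be 0%.

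**The case against.** The strongest reply is that this is rounding with no practical consequence. Much of that stands:

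- Rounding to a whole degree fits the storage section and is probably what happened.
- Neutropenia with a 38.4 °C fever is still reported and tabulated as an adverse event (Sections 8.1.2 and 9.4.2.1), whatever its DLT status.
- Table 8's discretionary entry lets the principal investigator and medical monitor call a treatment-limiting event a DLT. Grade 4 neutropenia that does not recover to Grade 2 or less within 7 days of interrupting treatment is a DLT at any temperature.
- Sections 4.1.1 and 5.4.1 allow interruption for toxicity without a DLT label.
- Section 5.4.3 lets investigators use any necessary measure in urgent situations, and Section 5.6.3 leaves the final decision on supportive therapy with the physician.
- High-grade events are adjudicated on calls between the sponsor and investigators (Sections 4.1.1, 5.4.5 and 8.8).
- Few DLT windows could still be open. With consent by 08 MAY 2018 and Day 1 within 21 days of consent (Section 6.2), the last Day 1 is 29 MAY 2018 and the last Day 42 is 09 JUL 2018, setting aside the one rescreen that Section 6.1 allows. Amendment 2 is dated 01 JUN 2018.

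None of this says which unit governs. A rounded figure is harmless in a storage range but not in a strict cut-off. The discretionary entry can add a DLT, but it does not settle this criterion, and the adjudication calls are given no temperature rule.

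**Conclusion.** The limit is wrong as written: two unequal values serve as one strict threshold, they disagree over 0.17 °C, and no governing unit is stated. The effect is limited to the DLT label of an in-band event and the three consequences that follow from it.

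Three stronger readings are tempting, and the documents do not support them:

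- A reader might infer that an in-band event drops out of the primary safety endpoint. It does not. Table 1 assesses that endpoint through adverse events, laboratory results, physical examinations and ECGs as well as DLTs, so only the DLT component could differ.
- A reader might infer that the recommended dose could be misjudged. Step 4 shows that one label can matter to Table 2, but with enrollment halted and neither backfill nor Phase 2 to open, little or no escalation remains to be affected.
- A reader might infer that a febrile neutropenic subject could be refused growth factor or kept on treatment. Sections 4.1.1, 5.4.1, 5.4.3 and 5.6.3 leave both to clinical judgment.

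The practical impact is very small. The 0% to 5.0% range rests on the assumptions in Step 5. It is not a bound on the true rate: an observed count of at most 3 in 294 does not cap that rate, it covers treatment-related events only, and its observation window is not stated to be 42 days. No sample size, alpha or power figure depends on this threshold.

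**What to change.** In Table 8, print the limit as **> 38.5 °C (101.3 °F)** and state that Celsius governs. The pair converts exactly, splits no reading, and agrees with the Celsius-only body temperatures in Tables 11 and 23. Apply the same rule when DLTs are classified and reported.

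If the lower limit was intended, print **> 101 °F (38.3 °C)** with Fahrenheit governing. That pair splits only a reading of 101.0 °F (38.33 °C), and naming the unit resolves it.

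The cost is one line and no new data collection. A formal protocol change needs sponsor and IRB/IEC approval (Section 10.1), so if no further amendment is planned, a clarification to sites and a stated rule for DLT reporting would be enough.
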